## 6.2 Study Restrictions

### 6.2.1 Concomitant Medications

Any medication taken within 14 days of study drug administration will be considered a concomitant medication. The site will also enter the patient's prior therapies for MF. Patients taking medications chronically should be maintained on the same dose and dosing schedule, if medically feasible.

Necessary supportive measures for optimal medical care will be given throughout the study, including intravenous antibiotics to treat infections, blood components, antidiarrheals, and antiemetics. Additional care will be administered as indicated by the treating physician and the patient's medical need. No concomitant cytotoxic therapy, whether conventional or investigational, will be allowed during this study. All concomitant medications and supportive therapy must be recorded in the eCRF.

Routine prophylactic use of growth factors (G-CSF, GM-CSF, and erythropoietin) or high dose steroids (>10 mg/day of prednisone or prednisone equivalent) is not permitted. Therapeutic use may be considered at the treating physician's discretion in patients who develop complications secondary to cytopenias (e.g., overt sepsis).

Blood products can be administered as needed.

The potential for drugs which are metabolized by cytochrome p450 enzymes being affected by NS-018 is considered possible. The plasma concentration of these drugs may increase or decrease when administered concomitantly with NS-018.

Patients currently taking medication that is substantially metabolized by cytochrome P450 (CYP) 1A2 or CYP3A4 (see Appendix E) are not eligible for this study. Every effort should be made to change these medications to acceptable alternatives to allow patient enrollment.

Patients taking strong CYP3A4 inducers or strong CYP3A4 inhibitors (see Appendix E) who cannot be safely switched to an acceptable alternative are excluded from the study.

If a patient requires administration of a medication that is substantially metabolized by CYP1A2 or CYP3A4 or requires the administration of a strong CYP3A4 inhibitor after enrollment, and is benefiting from study treatment, the NS-018 dose will be decreased by 50%. When the course of treatment with a medication that is substantially metabolized by CYP1A2 or CYP3A4 or is a strong CYP3A4 inhibitor has been completed, the patient will resume their previous dose of NS-018 beginning the next day.

Use of moderate or weak CYP3A4 inducers or moderate or weak CYP3A4 inhibitors (see Appendix E) is discouraged (alternative therapies should be considered), but does not disqualify the patient from study participation and does not require dose modification.

No other drugs that directly treat myelofibrosis are allowed during this study. No other investigational agents and anticancer agents are permitted while on study. Herbal medications should be discontinued and not initiated while participating in the study.

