9. QTcB  $\leq 480$  msec.
10. No MF-directed treatment for at least 2 weeks prior to initiation of NS-018, including any use of corticosteroids for Myelofibrosis symptom or blood count management. Low dose corticosteroids  $\leq 10$  mg/day prednisone or equivalent is allowed for non-myelofibrosis purposes.
11. No treatment with any investigational agent or anticancer agents within 2 weeks prior to initiation of NS-018.
12. Able to provide written informed consent prior to enrollment into the study.

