EMH, extramedullary hematopoiesis (no evidence of EMH implies the absence of pathology-or imaging study-proven nonhepatosplenic EMH); LCM, left costal margin; UNL, upper normal limit.

\*Baseline and posttreatment bone marrow slides are to be interpreted at one sitting by a central review process. Cytogenetic and molecular responses are not required for CR assignment.

†Grading of MF is according to the European classification

Thiele et al. European consensus on grading bone marrow fibrosis and assessment of cellularity. *Haematologica*. 2005;90:1128.

It is underscored that the consensus definition of a CR bone marrow is to be used only in those patients in which all other criteria are met, including resolution of leukoerythroblastosis. It should also be noted that it was a particularly difficult task for the working group to reach a consensus regarding what represents a complete histologic remission.

‡Immature myeloid cells constitute blasts 1 promyelocytes 1 myelocytes 1 metamyelocytes 1 nucleated red blood cells. In splenectomized patients, <5% immature myeloid cells is allowed.

§See above for definitions of anemia response, spleen response, and progressive disease. Increase in severity of anemia constitutes the occurrence of new transfusion dependency or a  $\geq 20$  g/L decrease in hemoglobin level from pretreatment baseline that lasts for at least 12 weeks. Increase in severity of thrombocytopenia or neutropenia is defined as a 2-grade decline, from pretreatment baseline, in platelet count or absolute neutrophil count, according to the Common Terminology Criteria for Adverse Events (CTCAE) version 4.0. In addition, assignment to CI requires a minimum platelet count of  $\geq 25000 \times 10(9)/L$  and absolute neutrophil count of  $\geq 0.5 \times 10(9)/L$ .

||Applicable only to patients with baseline hemoglobin of  $<100$  g/L. In patients not meeting the strict criteria for transfusion dependency at the time of study enrollment (see as follows), but have received transfusions within the previous month, the pretransfusion hemoglobin level should be used as the baseline.

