{Transfusion dependency before study enrollment is defined as transfusions of at least 6 units of packed red blood cells (PRBC), in the 12 weeks prior to study enrollment, for a hemoglobin level of  $<85$  g/L, in the absence of bleeding or treatment-induced anemia. In addition, the most recent transfusion episode must have occurred in the 28 days prior to study enrollment. Response in transfusion-dependent patients requires absence of any PRBC transfusions during any consecutive “rolling” 12-week interval during the treatment phase, capped by a hemoglobin level of  $\geq 85$  g/L.

#In splenectomized patients, palpable hepatomegaly is substituted with the same measurement strategy.

\*\*Spleen or liver responses must be confirmed by imaging studies where a  $\geq 35\%$  reduction in spleen volume, as assessed by MRI or CT, is required. Furthermore, a  $\geq 35\%$  volume reduction in the spleen or liver, by MRI or CT, constitutes a response regardless of what is reported with physical examination.

††Symptoms are evaluated by the MPN-SAF TSS. The MPN-SAF TSS is assessed by the patients themselves and this includes fatigue, concentration, early satiety, inactivity, night sweats, itching, bone pain, abdominal discomfort, weight loss, and fevers. Scoring is from 0 (absent/as good as it can be) to 10 (worst imaginable/as bad as it can be) for each item. The MPN-SAF TSS is the summation of all the individual scores (0-100 scale). Symptoms response requires  $\geq 50\%$  reduction in the MPN-SAF TSS.

‡‡Progressive disease assignment for splenomegaly requires confirmation my MRI or computed tomography showing a  $\geq 25\%$  increase in spleen volume from baseline.

Baseline values for both physical examination and imaging studies refer to pretreatment baseline and not to posttreatment measurements.

Source: Tefferi A, Cervantes, F, Mesa R, et al. Revised response criteria for Myelofibrosis: International Working Group-Myeloproliferative Neoplasms Research and treatment (IWG-MRT) and European LeukemiaNet (ELN) consensus report. *Blood*, 2013 122: 1395-1398

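### A hemoglobin rise (or Phase 1 platelet rise) sustained by transfusion or erythropoietin can be scored as clinical improvement, because these routes carry no on-study transfusion condition

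*Combined protocol and SAP*

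**What the plan says.** **Supportive care.** Section 6.2.1 states: "Blood products can be administered as needed". "Routine prophylactic use of growth factors (G-CSF, GM-CSF, and erythropoietin) or high dose steroids" above 10 mg/day prednisone equivalent is not permitted, but therapeutic use is left to the physician's "discretion in patients who develop complications secondary to cytopenias". The section also requires: "All concomitant medications and supportive therapy must be recorded in the eCRF".

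**Response rate.** Section 12.4 defines the ORR as the percentage of patients with confirmed CR, PR or CI, with an exact 95% interval by dose level. It has no rule for a response reached during transfusion or growth-factor use.

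**Phase 2 criteria (Appendix K).** Every benefit must last at least 12 weeks. For patients dependent at entry, the footnote says "Response in transfusion-dependent patients requires absence of any PRBC transfusions" in a rolling 12-week interval. Other patients with baseline hemoglobin below 100 g/L need a rise of at least 20 g/L. If they were transfused in the month before entry, "the pretransfusion hemoglobin level should be used as the baseline". Nothing similar is said about the on-study value. New transfusion dependency counts as worsening anemia and rules out CI.

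**Phase 1 criteria (Appendix I).** CI must last at least 8 weeks. It can be met by a hemoglobin rise, by becoming transfusion independent, or by a doubling of a platelet count that was below 50 × 10⁹/L. The two rises have no transfusion condition. Transfusion at a hemoglobin of 85 g/L or more is discouraged, not disqualifying.

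**The concern.** The adjustment is one-sided. Appendix K removes the effect of transfusion from the baseline hemoglobin of a recently transfused patient but not from the later value compared with it. Inclusion criterion 8 likewise requires the entry platelet count to be reached without growth factors or platelet transfusion, yet the Phase 1 platelet response has no such condition.

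With no control arm, a rise due to transfusion or erythropoietin cannot be told apart from a rise due to NS-018, and any error raises the ORR. Efficacy is part of the Phase 2 primary objective (Section 2.1.2), and the response rate is one input to the clinically active dose (Section 6.1.1).

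**Working it through.** **1. The plan's own figure.** Section 12.1 tabulates the chance of at least one event in 20 patients, 1 − (1 − p)²⁰. For p = 5, 10, 15, 20 and 30% this gives 64.2, 87.8, 96.1, 98.8 and 99.92%, matching the table (last entry printed as above 99.9%). This concern does not affect the table, which supplies N = 20.

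**2. Routes that transfusion could influence.**

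| Route | On-study condition | Status |
|---|---|---|
| App. K, dependent at entry | No red-cell transfusion for 12 weeks | Closed |
| App. K, newly dependent on study | No CI | Closed |
| App. K, rise of ≥20 g/L, not dependent at entry | None; baseline corrected only | Open |
| App. I, becoming transfusion independent | Built into the criterion | Closed |
| App. I, hemoglobin rise | None | Open |
| App. I, platelet doubling | None | Open |
| App. I, neutrophil doubling | Needs baseline ANC below 1 × 10⁹/L; entry needs above 1000/µL | Closed if baseline matches the entry value |

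The platelet route has eligible patients: entry allows 25,000/µL (25 × 10⁹/L) and the route applies below 50 × 10⁹/L. Its absolute floor is printed as 50,000 × 10⁹/L, 1,000 times the eligibility limit in the same item; I read it as 50 × 10⁹/L. The Appendix I hemoglobin threshold is printed as 2 g/L, against 20 g/L in Appendix K. The gap exists under either figure.

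**3. What the duration rule sees.** Cycle 4 Day 1 to Cycle 7 Day 1 is 3 × 28 = 84 days, or 12 weeks. Section 5.2 schedules hematology at C4D1, C4D15, C5D1, C5D15, C6D1, C6D15 and C7D1: seven values. From Cycle 7 to Cycle 10 there are four. One transfusion before a visit would therefore not clearly qualify; the rise has to be sustained.

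**4. Room below the dependency limit.** The only printed definition is the entry one: at least 6 units in 12 weeks, given for hemoglobin below 85 g/L. So 5 units, or units given at 85 g/L or more, fall outside it. Assume one unit adds 7 to 10 g/L (not in the documents). A 20 g/L boost then takes 20/10 = 2 units, or 20/7 = 2.9, rounded up to 3. Two full boosts take 4 units at 10 g/L per unit, but 6 at anything less. Transfusion alone thus supplies two boosts within the limit only at the top of the range. Less is needed if erythropoietin or a partial drug effect supplies part of the rise. Appendix I prints no block on CI for new dependency during treatment.

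**5. Effect per patient.** One response at N = 20 is 1/20 = 5 points. For illustration, 5/20 is 25.0% (exact 95% interval 8.7 to 49.1); one fewer, 4/20, is 20.0% (5.7 to 43.7). In a Phase 1 cohort one response is 1/6 = 16.7 or 1/3 = 33.3 points. A patient who also qualifies by another route stays a responder.

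**The case against.** The strongest reply is that the criteria already contain the main protections. Phase 2 blocks patients who are dependent at entry or become dependent. The 8- and 12-week durations, with interim hematology, defeat a short-lived boost. Growth factors are restricted, not freely available. The ORR is descriptive, with no hypothesis test. These points stand, and they reduce the likely number of affected patients. They do not close the open routes, because no text says that a hemoglobin value supported by transfusion is disregarded when duration is judged.

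Two further points are fair. Section 12 leaves the description of the analysis to a Statistical Analysis Plan. The text available contains no separate one, so a rule there cannot be excluded. Also, the Synopsis paragraph on statistical analyses defines the ORR by complete and partial responses only. Under that definition the open routes, all of which lead to CI, would not enter the ORR. The Synopsis efficacy paragraph and Section 12.4 include CI, and I have followed them.

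A reader might infer more than the documents support:

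- **Steroids produce symptom responses.** Criterion 10 counts MF-directed treatment as "including any use of corticosteroids for Myelofibrosis symptom or blood count management", and Section 6.2.1 bars other drugs that directly treat myelofibrosis, so the documents point away from such use. The symptom route exists only in Phase 2 and needs a 50% fall in the symptom score lasting 12 weeks.
- **CR and PR are inflated too.** Both also require symptom resolution and a non-palpable spleen and liver, which transfusion alone cannot supply.
- **Any growth factor should void a response.** The neutrophil route is closed by the entry count, and Appendix K has no neutrophil response. A G-CSF course gives no reason to void a hemoglobin rise.

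**Conclusion.** The concern holds for three routes: the Appendix I hemoglobin rise, the Appendix K hemoglobin rise in patients not transfusion-dependent at entry, and the Appendix I platelet rise. Through these, a rise sustained by transfusion, or a hemoglobin rise sustained by therapeutic erythropoietin, can be counted in the ORR.

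The size is 5 points per affected patient in Phase 2, provided all 20 patients are in the Efficacy Population at one dose level. The number affected is unknown and may be zero. A one-patient shift is small beside an exact interval about 40 points wide (49.1 − 8.7 = 40.4), but it acts in one direction and the interval does not reflect it.

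A reader might infer that supportive care in general is counted as drug effect, or that the clinically active dose will be wrongly chosen. The documents support neither: several routes are blocked, and Section 6.1.1 leaves that dose to a joint judgment of response and toxicity. The conclusion rests on the Section 12.4 definition of the ORR and on there being no counting rule elsewhere.

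**What to change.** Add to Section 12.4, or to the Statistical Analysis Plan:

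- A hemoglobin-rise response counts only if no red-cell transfusion and no erythropoietin was given during the qualifying window (8 weeks in Phase 1, 12 weeks in Phase 2).
- A Phase 1 platelet response counts only if no platelet transfusion was given during its 8-week window.
- Otherwise that component is scored as non-response; other routes to response are unaffected.
- The ORR and its exact 95% interval are shown by dose level with and without this rule.

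The rule changes counting only, not patient care. It is a derivation from transfusion and medication records that Section 6.2.1 already requires in the eCRF, assuming these carry dates and product type. The cost is a possibly slightly lower ORR and a rule stricter than the published criteria. Showing both versions keeps the result under the published criteria available for comparison.

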## **7 INVESTIGATIONAL PRODUCT**

### **7.1 Clinical Trial Material**

NS-018 will be supplied by NS Pharma.

The lot numbers and expiration dates (if available) of the drugs supplied will be recorded in the final report.

### **7.2 Pharmaceutical Formulation(s)**

NS-018 is provided in 25 mg and 100 mg film-coated tablets. The tablet contains 25 mg or 100 mg of NS-018 drug substance and the following inactive ingredients: microcrystalline cellulose, lactose monohydrate, croscarmellose sodium, hydroxypropyl cellulose, and magnesium stearate.

### **7.3 Administration**

The patient will be instructed to take study drug 2 hours or more after the last meal and at least 1 hour before the next meal. When the twice daily (BID) dosing schedule is initiated, NS-018 doses must be administered at least 12 hours apart.

### **7.4 Labeling and Packaging**

Open-label supplies will have a label indicating the number of tablets, storage conditions, directions for use, and sponsor study number and identification, as well as appropriate cautionary language for investigative material. Each bottle will contain 40 tablets. The labels will include space for the patient number and initials to be entered by the investigator.

### **7.5 Dispensing Procedures and Storage Conditions**

#### **7.5.1 Dispensing Procedures**

NS-018 will be dispensed to patients in high density polyethylene bottles with polypropylene caps containing 40 tablets. NS-018 will be dispensed at Cycle 1 Day 1 and all other applicable visits.

At each visit, patients will bring the bottles of study drug dispensed to calculate study drug compliance.

Patients will be instructed not to split, crush, or chew tablets.

**7.5.2 Storage Conditions**

NS-018 tablets should be stored away from light at 2 to 8 °C.

Study drug must be stored in a pharmacy or a locked and secure storage facility, accessible only to those individuals authorized by the investigator to dispense the investigational drug.

**8 SAFETY ASSESSMENTS**

**8.1 Adverse Events**

**8.1.1 Collection of Adverse Events**

It is responsibility of the investigator to collect all AEs (both serious and non-serious) derived by spontaneous, unsolicited reports of patients, by observation and by routine open questionings e.g., "How have you felt since I last saw you?"

**8.1.2 Definition of Adverse Events**

An AE is any untoward medical occurrence that occurs in a patient or clinical investigation subject administered a pharmaceutical product, and which does not necessarily have to have a causal relationship with this treatment. An AE can therefore be any unfavorable and unintended sign (including abnormal laboratory finding), symptom, or disease temporally associated with the use of an investigational product, whether or not considered related to the product.

Progression of disease is considered an efficacy outcome parameter and should not be captured as an AE.

All AEs, including intercurrent illnesses, occurring during the study will be documented in the eCRF. Concomitant illnesses, which existed before entry into the study, will not be considered AEs unless they worsen during the treatment period. All AEs, regardless of the source of identification (e.g., physical examination, laboratory assessment, ECG, reported by patient), must be documented.

Pre-existing conditions will be recorded in the eCRF on the Medical History or appropriate page.

A treatment-emergent AE (TEAE) will be defined as an AE that begins or that worsens in severity after at least one dose of study drug has been administered.

